6.3.5 Concomitant Medications

The use or change in dose of any medication ongoing or started from the randomization and up to the end of study is recorded on the eCRF. Concomitant medications are coded with respect to indication and generic name using the WHO drug dictionary (September 2016 or higher). Concomitant medications will be presented at randomization.

Frequency of use of medications at randomization will be presented by the level 2 Anatomical Therapeutic Chemical (ATC) classification and preferred term, for each treatment arm. Data will be summarized and presented as proportion of subjects overall and by treatment group receiving any drug in a treatment medication classification at the randomization visit.

A subject data listing of concomitant medications will also be provided.

6.3.6 Treatment Compliance

Accountability and subject compliance will be assessed by maintaining adequate drug dispensing and return records. Subjects will be asked to return all used and unused drug supply containers at each visit as a measure of compliance.

An overall compliance calculation will be performed using the study administration intake recorded. Compliance for the whole study is derived as follows:

$$\text{Compliance} = \frac{\text{\# days subject took study medication}}{\text{\# days in the study}} \times 100$$

days in the study = Date subject completed the study - date of randomization + 1.

Total time on study medication = Date of treatment last dose - date of treatment first dose + 1.

days subject took study medication (duration of treatment exposure) = Total time on study medication - the sum of all interruption durations for each record on the *Treatment Inter/ Disc* Form of the eCRF. It should be noted that only interruptions over 7 days are captured.

Subjects who died with no report of study drug discontinuation will be considered as discontinuing drug on date of death and date of treatment last dose will be imputed as date of death.

Compliance will be summarized by treatment arm using descriptive statistics.

Compliance will also be categorized as follow: < 80% or [80%-100%] and summarized accordingly using frequencies and percentages, by treatment arm, for the subjects of the ITT population.

Compliance results will be listed.

6.4 Efficacy Analysis

All efficacy analyses will be conducted on the ITT population.

6.4.1 Primary Analysis

A stratified Cox proportional hazards model will be used to analyze the primary endpoint. Time to event will start at randomization and subjects who are event-free will be censored at the time that they are last known to be event free. The strata, i.e., as those for randomization, will be defined by region (Eastern Europe, Western Europe, North America, South America and other) and the ACS index event (MI¹ or hospitalization for ACS [ECG abnormalities without biomarkers]). In case of a mismatch between the stratum assigned at time of randomization and the stratum confirmed in the eCRF, the stratum confirmed in the eCRF will be used.

More precisely, the Cox proportional hazards model will include treatment as a main effect, and region and ACS index event type as stratification factors.

The null and alternative hypotheses to be tested with the above Cox model are:

¹MI corresponds to the following two categories of ACS index event as collected in the eCRF: “Spontaneous myocardial infarction” and “Procedure-related myocardial infarction after percutaneous coronary intervention (PCI)”.

$$H_0: \lambda = 1 \text{ vs. } H_A: \lambda \neq 1$$

Where λ is the, assumed constant, hazard ratio for the time to occurrence of the composite events of the primary endpoint for the dalcetrapib and placebo treated groups. The hazard ratio, within strata, will be assumed to depend on treatment alone. The estimated hazard ratio will be presented with a 95% confidence interval (CI) and a p-value.

The primary analysis will be conducted at the 0.05 significance level.

For descriptive purposes, the number and percentage of subjects with each component of the composite primary endpoint will be presented. Time to event will also be graphically displayed using Kaplan-Meier curves.

A subject data listing of primary composite endpoint will also be provided.

6.4.1.1 Evaluation of Primary Endpoint Adjudication

In order to evaluate the consistency of subject outcomes as assessed by the investigator and as adjudicated by the CEC, the concordance between both assessments for the components of the primary endpoint will be summarized using descriptive statistics.

In addition, to go into more depth for death, types of death (CV, non-CV, undetermined), as reported by the investigator and as adjudicated by the CEC, will be summarized using descriptive statistics. No formal statistical testing will be done.

6.4.2 Secondary Analysis

Secondary endpoints are expressed as time to event and an analysis similar to that for the primary endpoint will be conducted.

In order to control the family-wise Type I error that results from the multiplicity of endpoints, the secondary endpoints described in section 4.2 will be formally tested using the Hochberg's step-up procedure only if the primary analysis results in significant treatment effect at $p < 0.05$. Otherwise, statistical tests for the secondary endpoints will be presented solely for illustrative purposes. See section 6.4.6.

Subject data listings will also be provided.

6.4.3 Exploratory Analysis

The changes from baseline to 6 months in TC, TG, LDL-C and HDL-C levels as well as in hsCRP will be compared between treatment groups using an analysis of covariance (ANCOVA) adjusting for baseline value and for the two stratification factors ACS index event type and region. Specifically, the null and alternative hypotheses to be tested are:

$$H_0: \Delta_{\text{placebo}} = \Delta_{\text{dalcetrapib}} \text{ VS.}$$

$$H_A: \Delta_{\text{placebo}} \neq \Delta_{\text{dalcetrapib}}$$

where Δ_{placebo} is the change in the placebo group and $\Delta_{\text{dalcetrapib}}$ is the change in the dalcetrapib group. Estimates of treatment effect will be presented with 95% CI and p-values.

Because it is expected that the distribution of hsCRP will be skewed, a log-transformation will be applied to hsCRP data prior to analysis. Geometric mean and geometric mean percent change will be added to the descriptive statistics that will be presented.

Since these analyses are exploratory, a conservative baseline observation carried forward approach will be used in subjects with missing 6-month value. Subjects with no baseline value will be excluded from the analysis.

6.4.4 Sub-population Analyses

For illustrative purposes, the following factors

- Region (Eastern Europe, Western Europe, North America, South America and other)
- Age (< 65, ≥ 65 to < 75, ≥ 75 years)
- Sex (Male, Female)
- Diabetes reported at baseline (Yes, No)

will be used to define subgroups of subjects within which the primary efficacy endpoints will be evaluated using non-stratified Cox proportional hazards models with a term for the treatment group, a term for the factor defining the subgroup and a term for the interaction between the factor and the treatment group. This interaction term will be tested at the 0.1 significance level and will determine whether the treatment effect is affected by the presence of the factor. In addition, under the proposed models, the treatment effect will be estimated and presented with 95% confidence intervals within subgroups.

6.4.5 Additional Analysis

6.4.5.1 Effect of HDL-C at baseline

In order to characterize the potential treatment effect more precisely, an analysis of the primary endpoint will be conducted with the hazard ratio assumed to depend on, in addition to treatment, baseline HDL-C.

Baseline HDL-C will be included in the stratified Cox proportional hazards model used for the primary analysis to provide an estimate of treatment effect that adjusts for HDL-C at baseline.

6.4.5.2 Sensitivity Analysis and Robustness Checks

If a statistically significant treatment effect is demonstrated in the analysis of the primary endpoint, the robustness of the results will be evaluated with respect to their potential dependence on the assumptions made.

- 1) The effect of censoring subjects who are lost to follow-up (while event-free), i.e. event-free subjects who do not have an end of study visit assessing efficacy endpoints after the start of the EOS visit window (common cut-off date), will be evaluated by imputing event outcomes for such subjects in the analysis. The following imputations rules will be considered.
 - a. It will be assumed that an event has occurred shortly after censoring so an event will be imputed at the date of censoring in all event-free subjects who will not have an end of study visit assessing efficacy endpoints after the start of the EOS visit window.
 - b. Imputed events will be based on a Weibull regression model that will be fitted to the subjects of the placebo group. This model will then be used to simulate a time to event in all event-free subjects (of both groups) who will not have an end of study visit assessing efficacy endpoints after the start of the EOS visit window (placebo-based imputation) [1]. If the simulated time to event is prior to the study cut-off date, it will be used as an imputed event. Otherwise, the subject will be censored at the study cut-off date. The entire process will be repeated by simulation and will generate multiple imputed datasets. On each imputed dataset, the Cox proportional hazards model used for the primary analysis will be applied and the resulting hazard ratios will be combined using Rubin's rule [2].
 - c. The third approach will be similar to b) above. The imputed events will be based on the same Weibull regression model fitted to the subjects of the placebo group. However, instead of using the survival distribution of that model to simulate time to events in subjects of both groups, the hazard of event will be increased by a factor δ ($\delta > 1$) when simulating time to events in dalcetrapib subjects (δ -adjusted hazard imputation) [1]. No such increase will be considered when simulating time to events in placebo subjects. The factor δ will be taken as the inverse of the expected hazard ratio (HR=0.78) and will be set to 1.3 [3]. As in b), the entire simulation process will be repeated and the resulting hazard ratios will be combined using Rubin's rule.
- 2) The primary analysis is based on a Cox proportional hazards model that assumes proportional hazards. The assessment of proportional hazard will be done by a visual inspection of the log-negative-log plot and through a formal test of the interaction between time and group at the 0.05 significance level.
- 3) The consistency of treatment effect across ACS index event types will be tested using the interaction term in a non-stratified Cox regression model that will include treatment, ACS index event type and treatment by ACS index event type interaction as main effects. The interaction test will be considered as indicative of a potential interaction in this exploratory analysis if $p < 0.1$. Estimates of treatment effect will be reported separately by strata, along with confidence intervals. The same approach will be used to examine the consistency of treatment effect across regions.
- 4) In the primary analysis, follow-up of primary efficacy endpoints will stop at the end of study visit. In other words, any primary efficacy endpoints collected between the end of study visit and the 14-day safety follow-up phone call will still be adjudicated but not be included in primary analysis.

However, as a sensitivity analysis, the primary analysis will be repeated, using the same model as described in section 6.4.1, but will include all adjudicated events, including those occurring between the end of study visit and the 14-day safety follow-up phone call.

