#### 8.2.4.3 Sensitivity Analyses

If a statistically significant treatment effect is demonstrated in the analysis of the primary endpoint, the robustness of the results will be evaluated with respect to their potential dependence on the assumptions made.

In particular, the effect of censoring subjects who are lost to follow-up (while event free) will be evaluated by imputing event outcomes for such subjects in the analysis. Various imputation rules will be applied and will be established prior to database closure and the breaking of the blind. The sensitivity of the primary analysis to treatments or procedures that would be expected to affect the primary endpoint will be assessed by additionally censoring such subjects at the time of the treatment or procedure.

The consistency of treatment effect across the ACS index event strata and across regions will be tested using a term of treatment by strata interactions in the Cox regression model. Interaction will be considered significant if  $p < 0.1$  and in the event that significant interactions are observed, estimates of treatment effect will only be reported by strata.

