
This is an event driven study and approximately 582 subjects with a primary event are needed to reach 85% statistical power assuming a 22% relative risk reduction in the primary endpoint. Subjects will be expected to remain in the trial until the time at which approximately 582 subjects have experienced a positively adjudicated primary event. We will model the accumulation of 582 first primary endpoints (a combination of adjudicated and completed probable packages), and inform the sites when we expect to have the start of the end of study visit window. All subjects who remain in the study (on or off study drug)

will be asked to return for an end of study (EOS) visit. Subjects still taking study medication at the EOS visit will also have a safety follow-up phone call 14 days after the EOS visit for the collection of adverse events, including components of the primary and secondary endpoints. All efficacy and safety events will be collected through the end of the trial.

The end of trial is defined as the date the last data point required for statistical analysis (i.e. key safety and efficacy results) is received, which corresponds to the end of study visit or the 14-day safety follow-up phone call, whichever is the latest. For the primary and secondary efficacy analyses (described in sections 6.4.1 and 6.4.2), follow-up of efficacy endpoints will stop at the end of study visit. In other words, any efficacy endpoints collected between the end of study visit and the 14-day safety follow-up phone call will still be adjudicated but not be included in primary and secondary efficacy analyses.

An independent Data Safety Monitoring Board (DSMB) will monitor the unblinded safety data during the study.

The schedule of assessments is presented in Table 1 below.

Table 1: Schedule of Assessments

Subjects who will be in the study for more than 3 years will continue to visit the clinic every 6 months and have the same assessments performed as during the second and third year.

	V1 Screening	V2 Day 0 (randomization)	V3 1M	V4 3M phone	V5 6M	V6 12M	V7 18M	V8 24M	V9 30M	V10 36M	End of Study VISIT	Phone 14 days after end of study visit
Visit windows (weeks)			± 1	± 3	± 3	± 3	± 4	± 4	± 4	± 4		+ 1
Informed Consent for Study Protocol	X											
ACDY9 genetic determinant (blood draw)	X											
Assessment of eligibility	X	X										
Demographic Information	X											
Query subjects for new/changes in contact information		X				X		X		X		

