6.3 Study Subjects

6.3.1 Subject Disposition

The number of randomized subjects, number of randomized subjects who took study medication, number of randomized subjects completing the study and reasons for study discontinuation will be summarized by treatment group. The number of subjects with survival status assessed at the end of the study will also be presented.

A flow chart following the recommendations of the Consolidated Standards of Reporting (CONSORT) statement will also be provided.

A subject data listing of subject disposition will be provided.

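### SAP 6.4.5.2 item 1 does not exempt subjects followed to a known non-CV death, so rule 1a imputes a primary event for them

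*SAP*

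**What the plan says.** Protocol 8.2.4.3 states the purpose of the check: "the effect of censoring subjects who are lost to follow-up (while event free) will be evaluated by imputing event outcomes for such subjects". SAP 6.4.5.2 item 1 keeps that label and then defines the set operationally as "event-free subjects who do not have an end of study visit assessing efficacy endpoints after the start of the EOS visit window".

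Three rules act on the set.

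- **Rule 1a:** "an event will be imputed at the date of censoring in all event-free subjects who will not have an end of study visit" assessing efficacy after the window opens.
- **Rule 1b:** a Weibull model fitted to the placebo arm simulates an event time for each of these subjects. A time before the cut-off counts as an event. "Otherwise, the subject will be censored at the study cut-off date".
- **Rule 1c:** as 1b, with the hazard multiplied by 1.3 in dalcetrapib subjects.

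The whole section is conditional: "If a statistically significant treatment effect is demonstrated in the analysis of the primary endpoint". SAP 6.4.6 says that analyses outside the primary and secondary hierarchy are interpreted descriptively.

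SAP 4.1 lists CV death as the only fatal component of the primary endpoint. SAP 4.1 and 6.4.1 censor event-free subjects when last known to be event-free. SAP 6.4.1.1 recognises CV, non-CV and undetermined deaths as separate adjudicated types. SAP 2.1 asks subjects still in the study to attend the EOS visit.

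**The concern.** The label and the definition do not describe the same people. A subject followed to an adjudicated non-CV death is not lost: endpoint status is known up to death, and no event can follow. Yet that subject is event-free, cannot attend an EOS visit and so meets every term of the definition.

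Rule 1a supposes that an unobserved event occurred just after censoring. That is a fair stress test for someone whose outcome is unknown, but it has no meaning for someone who has died. Applied as written, it mixes non-CV mortality into a check on loss to follow-up. With equal non-CV death rates the hazard ratio (HR) moves towards 1 on average. In a single trial, chance imbalance in deaths can move it either way, so the error is not reliably conservative. Rules 1b and 1c can simulate an event after a known death, or keep a dead subject at risk to the cut-off.

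**Working it through.** **1. Who is in the set.** Take a subject who dies of a non-CV cause before the EOS window.

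- Event-free? Yes: only CV death counts (SAP 4.1).
- EOS efficacy visit? None is possible.
- Exempted? No. SAP 4.1, 6.4.1 and 6.4.5.2 and Protocol 8.2.4.3 contain no exemption. The text of SAP 3.2 was not available, but the amendment table describes it as the definition of the ITT population.
- Censoring date? Last known event-free. For a subject followed to death this is naturally the date of death. If it is read as the last earlier contact, an event is still imputed, only on that date.

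**2. The plan's own figure.** Events = 4(z₀.₉₇₅ + z₀.₈₅)² / (ln 0.78)² = 4(1.960 + 1.036)² / 0.0617 ≈ 582, as stated. Power at 582 events is 85.0%. The issue does not affect this.

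**3. How many deaths could enter.** Inputs from SAP 6.1: 7% placebo event rate at 2 years, HR 0.78, 1% yearly loss, 2.8 years of recruitment, 6000 subjects. Protocol 3.1 gives 54 months (4.5 years) in total. Uniform accrual and exponential times are assumed.

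- Placebo hazard = −ln(0.93)/2 = 0.0363 per year; dalcetrapib 0.78 × 0.0363 = 0.0283.
- Person-years: 8,624 + 8,735 ≈ 17,359.
- Truly lost: −ln(0.99) × 17,359 ≈ 174.
- Non-CV deaths at assumed rates of 0.25%, 0.5% and 1.0% per year: about 43, 87 and 174.

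**4. Deaths alone, by ratio of rates.** Start from 582 events at HR 0.78, which is 257 dalcetrapib and 325 placebo. At 0.5% per year, add 43.7 and 43.1 deaths: HR = (300.6/8,735)/(368.2/8,624) = 0.806. The three rates give 0.794, 0.806 and 0.826. From a borderline observed HR of 0.84 (p = 0.036), they give 0.850, 0.859 and 0.874 (p = 0.043, 0.051 and 0.066).

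**5. Rule 1a by simulation.** There were 4,000 trials per setting, each with 6149 subjects randomised 1:1 and the inputs above. The Cox model was unstratified because stratum sizes are not given. Each trial had about 566 to 573 primary events on average. Only trials with primary p < 0.05 favouring dalcetrapib were kept (about 85%), since item 1 runs only then. Both versions of the set were applied to the same trials, with equal non-CV death rates in the two arms.

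| Assumed non-CV death rate per year | Deaths / lost | HR, lost only | HR, as written | Mean paired shift | 5th to 95th percentile of shift | Shift favours dalcetrapib |
|---|---|---|---|---|---|---|
| 0.25% | 44 / 178 | 0.813 | 0.823 | +0.010 | −0.014 to +0.034 | 25% |
| 0.5% | 88 / 177 | 0.813 | 0.831 | +0.018 | −0.014 to +0.050 | 18% |
| 1.0% | 175 / 176 | 0.813 | 0.845 | +0.033 | −0.010 to +0.076 | 9% |

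The Monte Carlo standard error is at most 0.0004 for the shifts and 0.0008 for the HR levels; small differences between columns are rounding. Known deaths make up 44/222 = 20%, 88/265 = 33% and 175/351 = 50% of the events rule 1a imputes.

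A purely hypothetical imbalance shows the direction. With 0.6% placebo and 0.4% dalcetrapib non-CV deaths per year, the HR goes from 0.813 to 0.797; reversed, it goes to 0.867. Nothing in the documents supports either case.

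**6. Rules 1b and 1c.** Under 1b the HR moves from 0.766 to 0.767, 0.768 and 0.769, with about 3, 5 and 10 events simulated after death. Under 1c it moves from 0.771 to 0.773, 0.771 to 0.775 and 0.770 to 0.779, with about 3, 6 and 12. These runs used 10 imputations, drew times after each subject's own censoring date and averaged the log HRs. Those are choices of the simulation, not of the SAP.

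**The case against.** The strongest reply is that the phrase lost to follow-up already excludes deaths in ordinary usage, and that rule 1a's premise cannot apply to someone who has died, so deaths were probably never meant to be in the set. That may well be the intent. But the operational definition follows immediately, and rules 1a and 1b repeat that they apply to all event-free subjects without the visit. A programmer builds the flag from that definition, and two programmers could build different sets. Where the SAP wants deaths handled in a particular way it can say so, as in its compliance section: "Subjects who died with no report of study drug discontinuation will be considered as discontinuing drug on date of death". That rule concerns the last-dose date and has no bearing on the imputation set, so it is only weak support.

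The second reply is that little depends on this. That largely stands. In a separate run of 2,000 trials per setting, imputing only the truly lost moved the mean HR from about 0.762 to 0.813, a shift of 0.051. The deaths add roughly 0.01 to 0.03 on top, usually in the conservative direction. Rule 1a is already an extreme scenario and has no pass/fail threshold.

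The third reply is that the size depends on non-CV death rates the documents do not give. That also stands, and it is why a range is shown.

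**Conclusion.** The concern holds. As written, item 1 treats subjects with complete follow-up to a non-CV death as lost, and rule 1a gives each of them a primary event. With equal assumed death rates of 0.25% to 1.0% per year, the mean rule 1a HR rises by 0.010 to 0.033; in 9% to 25% of trials the shift goes in dalcetrapib's favour. Rules 1b and 1c change by 0.009 at most. These sizes rest on the assumed death rates, uniform accrual, exponential times and an unstratified model. That the deaths fall in the set rests on the text alone.

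This is a point to consider, not a threat to the trial's conclusion. It concerns one descriptive sensitivity analysis, run only after a significant primary result.

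**What to change.** Add to SAP 6.4.5.2 item 1, for rules 1a to 1c:

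- Subjects whose endpoint status was followed up to a CEC-adjudicated non-CV death are not in the imputation set and stay censored at death. Say how they are recognised, for example by a last event-free date equal to the date of death.
- Subjects whose contact ended earlier and whose death was found only by a vital-status search (Protocol 5.5) stay in the set, with no simulated event after the date of death.
- Undetermined deaths follow their classification for the primary endpoint. SAP 4.1 does not state that classification, so cite where it is set.

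The cost is a short addition to the SAP and one population flag. The data are already needed for planned outputs: CEC death type (SAP 6.4.1.1), last event-free date (SAP 4.1) and survival status, for which SAP 6.3.1 says "The number of subjects with survival status assessed at the end of the study will also be presented". The primary analysis and sample size are untouched. Protocol 8.2.4.3 requires the imputation rules to be settled before database closure and unblinding, so the clarification belongs before that point; deciding afterwards whether deaths count would depend on the data.
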